Continuous toxicity monitoring based on repeated significance testing with a Pocock boundary will be applied after the first 5 patients have been accrued and evaluated for toxicities within an arm. The toxicity monitoring will be conducted within each of the two study arms. A toxicity rate p0 of at most 15% of Grade ≥ 3 toxicity events will be considered as acceptable while a toxicity rate p1=35% or more will be considered as unacceptably high. Assuming a boundary probability of 0.1 under p0, the stopping boundaries of the repeated significance testing procedure within an arm are as follows: 2/5, 3/9, 4/13, 5/17, 6/22, 7/26, or 8/30. If the number of Grade ≥ 3 toxicities exceeds the boundaries, i.e., ,if at least 3 out of the first 5 patients, at least 4 out of the first 6-9 patients, at least 5 out of the first 10-12 patients, at least 6 out of the first 13-17 patients, at least 7 out of the first 18-22 patients, at least 8 out of the first 23-26 patients, at least 9 out of the first 27 to 30 patients, at least 10 out of the first 31-35 patients or at least 11 out of the first 36 to 40 patients have been accrued and evaluated for toxicities within an arm.

Evidence that the toxicity rate of unusual or specific immune-related AEOSI within an arm excessive will be considered as sufficient if during any stage of the trial (after the accrual of the first 5 patients) the lower limit of the 90% one-sided confidence interval for the estimate of the true toxicity rate exceeds 10% for Grade \geq 3 or 5% for Grade \geq 4 toxicities within an arm.

If one of these thresholds is reached, accrual will be temporarily suspended and the study will be reviewed for safety, dose modification and safety modification, and the study will be reviewed for safety by the UW DSMC (data and safety monitoring committee) with respect to treatment arm. Once the study is suspended, it would only be reopened if modifications could be made, and approved by the DSMC and the UW-IRB, to assure that patient safety is reestablished. If not, the study would be closed.

Endpoints

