Patients who, in the discretion of the treating physician, appear to be benefiting (e.g. declining serum PSA and/or improvement in symptoms despite new radiographic lesions), may continue in protocol treatment after discussion with the sponsor PI. Some subjects may receive NaF PET/CT scans as a standard alternative to bone scintigraphy, in which case these will be used to determine response/progression. Patients will continue to have blood drawn for immune studies, as per study calendar, up to one year after screening, even if off study prior to that time. In particular, evaluations performed at 6-month time point should be performed even if off-study prior to that time, if feasible. At the end of 6 months, patients without progression will continue to receive pembrolizumab every 3 weeks, up to 2 years (32 cycles) maximum, or until radiographic disease progression. Patients on pembrolizumab alone who have PSA rise (25% increase over month 6 value, and minimum of 2 ng/mL rise) will resume a 3-month (4-cycle) follow-on course of vaccine treatment. The goal here is to minimize treatment but maintain a prolonged time to radiographic progression. All subjects who have not come off study earlier for reasons of adverse events, physician/patient discretion or radiographic progression will come off study at the end of two years of total treatment.

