A treatment-limiting toxicity will be defined as any Grade 3 or greater toxicity (using the NCI Common Terminology Criteria version 4), or a specific Grade 2 event as described below that affects agent dosing, with an attribution of at least possibly related to the study or treatment procedures, and occurring between the pre-study visit and within one month of the final study vaccine treatment or within 90 days of the last treatment with pembrolizumab (whichever is later). If a patient develops Grade 3 toxicity with an attribution of at least possibly related to pembrolizumab and unlikely related (or unrelated) to pTVG-HP or pTVG-AR vaccine, the pembrolizumab treatment will be held until the toxicity resolves to Grade 1 or less, with the vaccine schedule continuing as per protocol. If the adverse event is considered immune-related, both pembrolizumab and pTVG-AR (and/or pTVG-HP) will be held until the toxicity resolves to Grade 1 or less. If a patient develops a second Grade 3 event (or any Grade 4 event) believed to be at least possibly due to pembrolizumab, but unlikely related (or unrelated) to pTVG-HP or pTVG-AR vaccine, no further pembrolizumab treatments will be given. The patient will continue with DNA vaccine administration only as per protocol, if the adverse event is not immune-related. If immune-realted, both the pembrolizumab and vaccine(s) will be discontinued. However, if a patient develops a Grade 3 toxicity with an attribution of at least possibly related to pTVG-HP or

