The ITT population consists of all patients who are randomized. The per-protocol population consists of all evaluable patients, i.e., patients who have been treated according to protocol (all inclusion/exclusion criteria are satisfied, and adequate treatment compliance (complete treatment with pTVG-HP DNA vaccine alone or in combination with pTVG-AR DNA vaccine and Pembrolizumab to at least week 12). The safety population consists of all subjects who received at least one dose of pTVG-HP DNA vaccine with or without pTVG-AR DNA vaccine and Pembrolizumab. All primary, secondary and correlative outcomes will be analyzed for both the IIT and per-protocol population. The IIT population will be the primary analysis population. Safety will be evaluated using the safety population.

To attain 60 evaluable participants, the trial may randomize more than 60 participants if any are deemed unevaluable.

iii. Baseline Comparability

All measurements (variables) collected at baseline will be summarized and compared between study arms. These include demographic variables, ECOG PS, lab parameters (CBC, chemistry panel, serum testosterone, PSA and PAP) medical history information and CTCs. Comparisons between study arms of baseline variables on a continuous scale will be performed using a two-sample t-test and/or nonparametric Wilcoxon Rank Sum test. Comparisons between study arms of baseline variables on a categorical scale will be performed using a chi-square or Fisher's exact test.

iv. Analysis of Primary Endpoint

The 6-month PFS rate will be calculated for each study arm along with the corresponding two-sided 95% confidence interval which will be constructed using the Wilson score method. Patients who withdraw from the study without a progression or death event before the 6-month assessment will be excluded from this analysis. The stratified (by randomization strata) Mantel-Haenszel test will be used to compare the 6-months PFS rates between study arms.

v. Analysis of Secondary Endpoints

F.5.1. Overall Objective Response Rate and PSA Response Rates

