Subjects will be evaluated at each visit by a review of systems based on the most recent version of the NCI common toxicity criteria. Furthermore, serum chemistries, including renal function tests, blood counts, liver function tests, and serum amylase, will be evaluated at 6-12 week intervals. Toxicities will be summarized by type and severity in tabular format. Toxicity rates (grade 2, grade 3, grade 4, grade \geq 2, grade \geq 3, etc.) will be calculated for each study arm and reported along the corresponding 95% confidence intervals. The 95% confidence intervals will be constructed using the Wilson score method. Fisher's exact test will be used to compare toxicity rates between study arms. Serum chemistry and amylase parameters will be summarized using standard descriptive statistics. Changes from the baseline assessment will be evaluated using a paired t-test.

vi. Exploratory Analyses

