
- 0 No adverse event or within normal limits
- 1 Mild adverse event
- 2 Moderate adverse event
- 3 Severe adverse event
- 4 Life-threatening or disabling adverse event
- 5 Fatal adverse event

All adverse events will be recorded from time of treatment initiation through 30 days after the final dose of study treatment, as well as any time after these 30 days for events that are believed to be at least possibly related to study treatment. Please note: SAEs,

regardless of relationship, occurring from the time of consent until 90 days after the final dose of pembrolizumab will be collected and reported as per section E.1.

Appropriate clinical, diagnostic, and laboratory measures to attempt to delineate the cause of the adverse reaction in question must be performed and the results reported. All tests that reveal an abnormality considered to be drug- or vaccine-related will be repeated at appropriate intervals until the course is determined or a return to normal (or pretreatment) values occurs. Information will be recorded as noted above.

B. Disease Oriented Team Meetings

UWCCC site: This study undergoes review of subject safety at regularly scheduled Disease Oriented Team (DOT) meetings where the following are discussed as applicable: number of subjects enrolled, subject treatments given, dose holds/modifications, significant toxicities, response to treatment, and the subjects' overall status. These discussions are documented in the DOT meeting minutes.

C. UWCCC Data and Safety Monitoring Committee (DSMC) Study Progress Review and Oversight

The review of Protocol Summary Reports (PSRs) enables the UWCCC DSMC to assess whether the study should continue, continue with modifications, be suspended, or be closed. Following their review, the UWCCC DSMC will notify the sponsor-investigator of their recommendation and the authority for continuing, modifying, suspending, or closing the protocol is the responsibility of the applicable sponsor-investigator, Principal Investigator, IRB, FDA or other regulatory authority associated with the protocol.

Based on the risk level of this study, as determined by the UWCCC Protocol Review and Monitoring Committee, PSRs must be submitted to the UWCCC DSMC by the UWCCC site on a quarterly basis.

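### Grade ≥3 toxicity is compared as crude proportions and monitored against 15%/35% limits with no stated time base, although time at risk follows PFS; a common fixed period would remove most of the imbalance at little cost

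*Combined protocol and SAP*

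**What the plan says.** Section 11, F.5.4: toxicity rates by grade "will be calculated for each study arm and reported along the corresponding 95% confidence intervals", by the Wilson method, and Fisher's "exact test will be used to compare toxicity rates between study arms". The denominator is defined under Analysis Populations: "The safety population consists of all subjects who received at least one dose", whatever the exposure. No fixed period, time-to-event or person-time analysis of toxicity is planned.

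Section 6 (Endpoints): patients without progression at 6 months continue pembrolizumab "up to 2 years (32 cycles) maximum, or until radiographic disease progression".

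Section 6 (toxicity assessment): a Pocock-type boundary is applied within each arm, with 15% acceptable, 35% unacceptable and a crossing probability of 0.1 at 15%. The worded limits begin "at least 3 out of the first 5 patients, at least 4 out of the first 6-9 patients" and continue to 40 patients. The period over which a patient is evaluated is not given.

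The toxicity windows found elsewhere move with treatment duration. Section 8 defines a treatment-limiting toxicity as one occurring up to "within one month of the final study vaccine treatment or within 90 days of the last treatment with pembrolizumab", whichever is later. Section 13 says: "All adverse events will be recorded from time of treatment initiation through 30 days after the final dose of study treatment", with events judged at least possibly related recorded at any later time.

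**The concern.** A proportion of patients who ever had an event grows with time at risk. Here time at risk is tied to the primary endpoint: the arm with longer PFS stays on treatment longer. Extra toxicity from the second vaccine is the protocol's own stated worry about Arm 2, and safety is secondary objective 7. The crude comparison cannot separate a more toxic regimen from a longer one.

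The boundary has a related gap. A 15% rate over 24 weeks and a 15% rate over 22 months are different hazards, so without a stated period the 15%, the 35% and the 0.1 have no fixed meaning. The promised detailed SAP could repair the final comparison. It could not repair the boundary, which operates during accrual.

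**Working it through.** **The plan's own figure.** I applied the worded limits from patient 5 onward with an exact binomial recursion. At a true rate of 15%, the crossing probability is 0.0887 over 30 patients and 0.0993 over the 40 listed. The stated 0.1 is reproduced as a ceiling. (The listed fraction 4/13 disagrees with the worded limit at 13 patients. Using the fractions gives 0.0915 over 30, which does not affect this point, but the two should be reconciled.)

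**Inputs from the documents.** 6-month PFS 25% (middle of the stated 20-30%) and 55%; 30 patients per arm; 30 months of accrual, so one patient per arm per month; cap of 32 × 21 = 672 days, or C = 22.1 months; 90-day tail, taken as 3 months.

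**Assumptions, not in the documents.** Exponential time on treatment that matches PFS, and the same Grade ≥3 hazard h in both arms.

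**Time on treatment.** Leaving rates are l₁ = ln(1/0.25)/6 = 0.2310 and l₂ = ln(1/0.55)/6 = 0.0996 per month. The mean (1 − e^(−lC))/l is 4.3 months in Arm 1 and 8.9 months in Arm 2.

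**Crude toxicity, constant hazard.** P = 1 − e^(−3h) × [ l/(l+h) × (1 − e^(−(l+h)C)) + e^(−(l+h)C) ]. Setting Arm 1 to 15% gives h = 0.02285 per month.
- Arm 1: 1 − 0.9337 × (0.9100 × 0.9963 + 0.0037) = 15.0%.
- Arm 2: 1 − 0.9337 × (0.8134 × 0.9331 + 0.0669) = 22.9%.

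**Consequences.**
- Boundary, every patient followed to the end: crossed in 8.9% (Arm 1) and 36.3% (Arm 2).
- Boundary in calendar time, 30 months of accrual (40,000 simulated trials): about 3% and 10%.
- Fisher's test, two-sided p ≤ 0.05: 6.4% of trials, against 1.7% if both arms were truly at 15%.

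**Sensitivity.** Crossing is with complete follow-up.

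| Scenario (3-month tail) | Arm 1 | Arm 2 | Crossing, Arm 1 / Arm 2 |
|---|---|---|---|
| Constant hazard | 15.0% | 22.9% | 8.9% / 36.3% |
| Same, Arm 1 PFS 20% to 30% | 15.0% | 24.5% to 21.4% | 8.9% / 43.5% to 29.8% |
| Constant hazard, all treated at least 3 months | 15.0% | 19.3% | 8.9% / 21.5% |
| Declining hazard (0.06 per month at start, decay constant 3 months), at least 3 months' treatment | 15.0% | 15.6% | 8.9% / 10.2% |

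**Two possible remedies under the same hazards.**
- *Common fixed period.* Over 6 months from first dose, the constant hazard gives 11.1% and 12.0%, with crossing about 3% and 4%. The declining hazard gives 14.4% in both arms. If 15% is instead the rate within the period, crossing is 8.9% in both arms.
- *Person-time rate ratio.* This equals 1.0 under a constant hazard. Under the declining hazard above it is 0.70, although toxicity is identical by design. With 0.045 per month at start and decay constant 6 months it is 0.76.

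**Off-treatment time matters.** At a constant 0.03 per month with only on-treatment events counted, the whole-course proportions are 11.4% and 21.8%, a ratio of 1.91. A 24-week window that still counts only on-treatment events gives 8.8% and 11.9%, a ratio of 1.35. The period has to run from first dose whether or not the patient is still treated.

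**The case against.** The case against is substantial.

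- **A crude proportion is a legitimate estimate** of risk over the whole regimen. This stands. The gap is that nothing accompanies it.
- **The arms largely share their first three months.** Section 6 says the 3-month scan does not force discontinuation, and the initial vaccine course is confined to cycles 1-8. If toxicity is early, there is little to correct. This stands and limits the size.
- **A reader might infer that Section 6 counts events over each patient's whole time on treatment.** It does not say so. The Section 8 window belongs to a definition used for holding treatment, includes some Grade 2 events, and is not cited in the boundary rule. What the text supports is that the period is unstated.
- **A reader might infer that the more effective arm would probably be stopped.** At 0.03 per month, Arm 2 crosses at some time in about 20% of trials (on treatment) or 51% (with the tail). Those figures include crossings after enrolment is complete; by month 30 they are about 10% and 27%. Crossing also leads to suspension and review by the DSMC with respect to arm, not automatic closure.
- **A reader might infer that Fisher's test would often give a false alarm.** At 30 per arm it has too little power for that. The harm in F.5.4 is a misleading estimate.
- **A reader might infer that dividing by person-time gives the right answer.** It does so only under a constant hazard. Otherwise it can make the longer-treated arm look safer than it is.
- **A detailed SAP is promised before final analysis.** That answers the F.5.4 part if it is used, but not the boundary.

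**Conclusion.** The point holds as a cheap improvement. The planned comparison and the boundary both leave time at risk uncontrolled, and under the trial's own hypothesis time at risk differs between arms. Arm 2 had the higher crude rate in every equal-hazard scenario tried.

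The size is uncertain. It ranges from 15.0% against 22.9%, with boundary crossings during accrual of about 3% and 10% (constant hazard), down to 15.0% against 15.6% (mainly early toxicity). These figures rest on an assumed hazard shape, exponential time on treatment and the 90-day tail; the documents give no toxicity timing. They do not show that the plan would stop an effective arm or declare a false safety difference.

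**What to change.** 1. **Section 6 boundary.** State one common evaluation period from first dose, the same in both arms, for example the length of cycles 1-8. Count each patient's first Grade ≥3 toxicity within it, including off-treatment follow-up inside the period. State that 15%, 35% and the 0.1 refer to that period. Later events continue to go to the DSMC.
2. **F.5.4.** Keep the crude whole-course rates and Fisher's test. Add a between-arm comparison over the same period, or of time to first Grade ≥3 toxicity (log-rank test or cumulative incidence, censoring at the end of the at-risk window). Do not make a single person-time rate ratio the main comparison.

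The cost is a few lines in Section 6 and in the SAP. Adverse events are already recorded, including related events after treatment ends. The downside is that late events do not feed the count boundary, so their reporting to the DSMC should be stated explicitly.

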- ^f Where chemistry labs indicated, the following serum tests are to be performed: Chem 7 (sodium, potassium, bicarbonate, BUN, creatinine, glucose), ALT, AST, total bilirubin, alkaline phosphatase, amylase, creatine kinase (CK), TSH (thyroid stimulating hormone), LDH and cortisol (cortisol only required on treatment days and not at screening, EOT or 28 day follow up)
- g Procedures for cycle 5 day 1 ONLY can be +/- 7 days of this visit, NaF PET/CT scans to be done prior to biopsy for patients receiving biopsy
- ^h Can be +/- 7 days of this visit
- ⁱ Can be +/- 7 days of this visit, and not required if this is off-study visit and previous scans already confirmed disease progression ^j CT of chest at this time point only as clinically indicated
- ^k PT/INR and PTT only required for those subjects who will be undergoing a biopsy and only required at biopsy timepoints (screening and C5D1). May be performed up to 7 days prior to biopsy, required same day if subject is on coumadin. PT and/or INR may be done.
- ¹ If NaF PET/CT is available as standard of care procedure, this may be substituted for bone scan (bone scintigraphy), however all pre-treatment and post-treatment tests must use the same modality (NaF PET/CT or bone scintigraphy)
- m Biopsy can be performed +/- 14 days of this visit
- ⁿ For Arm 2, Subjects will receive pTVG-AR vaccine on days 1 and 8 of Cycles 1, 2, 5, and 6 and days 1 and 8 of Cycles 1 and 2 of the vaccine booster cycles (if applicable). Subjects will receive pTVG-HP vaccine on days 1 and 8 of Cycles 3, 4, 7, and 8 and days 1 and 8 of Cycles 3 and 4 of the vaccine booster cycles (if applicable).
- °CT of abdomen and pelvis (+/- chest as clinically indicated) and bone scintigraphy continue every ~12 weeks, +/- 7 days from visits at day 1 of cycles 13, 17, 21, 25, and 29
- ^p 100 mL green top tubes and 10 mL red top tubes collected at day 1 of cycles 13 and 17.
- ^q Blood for immune analysis only collected if not previously collected within 60 days
- MRI imaging may substitute for CT, but the same type of imaging must be used to determine eligibility and progression
- ^s Treatment cycles are defined as 21 days.

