receive two vaccines, and hence there is a theoretical possibility of increased toxicity in that arm. Therefore patients will be evaluated for evidence of toxicity, and further accrual to a specific treatment arm will be discontinued if the toxicity rate is deemed to be excessive for that arm. In addition, each of the first 6 patients randomized to Arm 2 will be staggered to start at least 3 weeks after the preceding patient assigned to that study arm. In this way, toxicity will be able to be monitored over at least 18 weeks in a smaller number of patients. If there are no adverse events > grade 2 that are not attributed to pembrolizumab alone, subsequent enrollment will proceed without staggering accrual. In addition, given that over 40 patients have been treated with the single pTVG-HP vaccine and pembrolizumab in a separate trial, and there have been no adverse events > grade 2 that were not attributed to pembrolizumab alone, there will be no staggering of accrual for patients assigned to Arm 1. Given the AE profile for pembrolizumab, a total toxicity rate of 50% for Grade \geq 3 events (or 20% for Grade \geq 4 events) with an attribution of at least possibly related to study treatment will be considered excessive. Grade 3 limited site reactions (lasting < 48 hours) and fevers/chills (lasting < 48 hours) will be excluded from this assessment, as expected possible adverse events of limited duration from vaccination. To monitor for particular toxicities that might arise from combination therapies, an adverse event rate of 10% for Grade > 3 or 5% \geq Grade 4 unusual or specific immune-related AEOSIs with an attribution of at least possibly related to study treatment will also be considered excessive.

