A sample size of 60 evaluable patients (30 per arm) is proposed for this study. The following table shows the attainable power levels for detecting various differences in the 6-months PFS rates between arms with a sample size of 30 patients per arm at the one-sided 0.10 significance level.

Attainable power levels for detecting various differences in the 6-months PFS rates					
between arms with the proposed sample siz	e of 30 patients	per arm			
6-months PFS rate in Arm 2					
6-months PFS rate in Arm 1	0.50 0.55 0.60				
0.20	88.8%	94.8%	98.0%		
0.25	77.1%	87.4%	94.1%		
0.30	62.0%	75.8%	86.6%		

Hence, the proposed sample size of 60 evaluable patients will provide 77-98% power to detect an anticipated difference in the 6-months PFS rates of 20-25% in Arm 1 vs. 50-60% in Arm 2. Analogously, the sample size will provide between 62-94% power to detect a difference of 25-30% in Arm 1 vs. 50-60% in Arm 2. PASS software (NCSS, LLC) version 12 was used to conduct the samples size calculations.

w. Analysis

i. General

This section outlines the statistical analysis strategy and procedures for the study. Prior to the analysis of the final study data, a detailed Statistical Analysis Plan (SAP) will be written describing all analyses that will be performed.

Summary tabulations will be presented that will display the number of observations, mean, standard deviation, median, range, minimum, and maximum for continuous variables and the number and percent per category for ordinal and categorical data. All endpoints of this study will be presented graphically where possible using boxplots and histograms for continuous variables and (stacked) bar charts for categorical variables. Data analysis will be performed using SAS® (SAS Institute Inc., Cary, North Carolina) version 9.4 or greater.

There are many comparisons made between the two trial arms for multiple measurements, both clinical and laboratory. However, since this is an early phase efficacy trail, no adjustment will be made for multiple comparisons.

ii. Analysis Populations

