13. DATA AND SAFETY MONITORING PLAN

A. Definitions

Adverse events (AE) are defined as any unfavorable and unintended sign (including abnormal laboratory finding), symptom or disease temporally associated with a medical treatment or procedure, regardless of whether it is considered related to the treatment or procedure. Adverse events are categorized as definite, probable, possible, unlikely or unrelated in relation to the medical treatment or procedure performed.

AEs include the following:

- 1. An exacerbation, or an unexpected increase in frequency or intensity of a pre-existing condition (other than condition under investigation), including intermittent or episodic conditions.
- 2. Significant or unexpected worsening or exacerbation of the condition/indication under investigation.
- 3. A suspected drug interaction.
- 4. An intercurrent illness.

5. Any clinical significant laboratory abnormality.

An AE does not include:

- 1. Anticipated day-to-day fluctuations of any pre-existing conditions, including the disease under study.
- 2. Signs and symptoms of the disease under study that do not represent a significant worsening or exacerbation.
- 3. Expected progression of the disease under investigation.
- 4. Abnormal laboratory findings that are grade 1 or 2 and are considered clinically insignificant.

Serious adverse events (SAE) are any events occurring that result in any of the following outcomes:

- 1. Subject death
- 2. Life-threatening adverse event
- 3. Inpatient hospitalization or prolongation of existing hospitalization
- 4. Persistent or significant disability/incapacity
- 5. Congenital anomaly or birth defect

A life-threatening event is defined as any adverse event that places the subject, in the view of the investigator, at immediate risk of death from the reaction.

Note: In addition to the above criteria, adverse events meeting any of the below criteria, although not serious per ICH definition, are reportable to the Merck in the same timeframe as SAEs to meet certain local requirements. Therefore, these events are considered serious by Merck for collection purposes.

- Is another important medical event
- Is a new cancer (that is not a condition of the study)
- Is associated with an overdose.

Severity rating/grading scale

Adverse events are classified by organ system and graded by severity according to the current NIH Common Terminology Criteria V. 5, as described in Appendix A. The defined grades use the following general guidelines:

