With respect to those subjects in Arm 2 also receiving immunization targeting the androgen receptor (AR), there is a theoretical risk of unwanted immune reactions to tissues expressing the AR. The androgen receptor is expressed at highest levels in prostate tissue, but is also expressed in other tissues, notably bladder, skeletal muscle, liver, testis, and brain. Thus it remains theoretically possible that autoimmune reactions could occur to these tissues. Of note, we have previously identified that patients with prostate cancer can have existing immune responses specific for the AR LBD, and do not have evidence of autoimmune toxicity [53]. Thus it is also conceivable that immune responses could be elicited without evidence of toxicity. We have also immunized tumor-bearing mice for up to one year, and observed an increase in survival without evidence of toxicity. However, in order to evaluate potential toxicity in humans, subjects will be evaluated at each visit by a review of systems based on the NCI common toxicity criteria. In addition, subjects will be examined and serum chemistries, including renal function tests, blood counts, liver function tests, will be evaluated at regular intervals, as outlined above. The serum creatine kinase level will be used as a serum marker to monitor for evidence of subclinical muscle toxicity, and serum measures for evidence of liver dysfunction will also be monitored. Subjects with evidence of autoimmune disease believed to be secondary to the immunizations will be taken off study and treated with corticosteroids (if required), as described above.

While there has been a suggestion that the plasmid DNA could insert into the host chromosomal DNA, this has not been documented in any other study, and several laboratory investigations have suggested the possibility of this occurring is less than the spontaneous mutation rate, and therefore

not a real risk [98]. Even should this occur, there is little reason to suspect that this would put subjects at any increased risk, and in this patient population with treated prostate cancer, there is little risk of transfer to offspring. There are no known risks to blood donation during or after immunization, however subjects will be requested to not donate blood from study entry until completion of all study procedures.

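### The only named test of continuous serum chemistry change is before versus after, so changes in CK and liver tests below the adverse-event threshold are not compared between arms

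*Combined protocol and SAP*

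**What the plan says.** F.5.4 treats safety data in two ways. For graded toxicities, rates are given by arm with Wilson 95% intervals, and "Fisher's exact test will be used to compare toxicity rates between study arms". For serum chemistry, values are summarised descriptively and "Changes from the baseline assessment will be evaluated using a paired t-test". The sentence does not say whether the test is run by arm or pooled, at which visit, or on which scale.

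Four other places bear on this.

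- Section 11.w.i says, in connection with multiplicity: "There are many comparisons made between the two trial arms for multiple measurements, both clinical and laboratory". It names no method for laboratory change and promises a detailed SAP before the final analysis.
- Section 13.A lists what is not an adverse event, including: "Abnormal laboratory findings that are grade 1 or 2 and are considered clinically insignificant".
- Section 14.aa.i, on the AR vaccine, says: "The serum creatine kinase level will be used as a serum marker to monitor for evidence of subclinical muscle toxicity". It adds that "serum measures for evidence of liver dysfunction will also be monitored".
- Section 6 notes that Arm 2 patients get two vaccines, "hence there is a theoretical possibility of increased toxicity in that arm".

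On exposure, the Arm 2 calendar states: "For Arm 2, Subjects will receive pTVG-AR vaccine on days 1 and 8 of Cycles 1, 2, 5, and 6". Arm 2 receives pTVG-HP in cycles 3, 4, 7 and 8. Arm 1 receives pTVG-HP in all eight cycles.

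**The concern.** Secondary objective 7 asks about safety with or without pTVG-AR, and section 6 puts the worry at arm level. CK is monitored for muscle injury that is subclinical. A subclinical shift is unlikely to be counted as a toxicity: a grade 1-2 value judged insignificant is not an adverse event, and in an open-label trial that judgement is made knowing the arm. The continuous values are where such a shift would show.

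The test named for those values compares each patient with his own baseline. Both arms receive pembrolizumab, for which the protocol lists immune-mediated hepatitis, and both share disease course and time on study. A significant paired change in Arm 2 would not show that Arm 2 differs from Arm 1. A pooled paired test would not address the arms at all. Section 11.w.iii does compare the chemistry panel between arms at baseline, where randomisation leaves only chance differences. No such comparison is specified after treatment. What is at stake is how a secondary safety result is read.

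**Working it through.** **The plan's own figures.** The plan gives no figure on this point. The 30 per arm comes from section 11.v, whose nine stated powers reproduce to 0.1 percentage point (pooled-variance z test, one-sided 0.10; for example 87.4% for 25% against 55%).

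**Assumptions.** The documents give no SD or drift for any analyte. Assumed: lognormal values; between-patient geometric SD 1.6; within-patient geometric SD 1.2, 1.35 or 1.5 at each visit; 30 per arm; two-sided 0.05; 20,000 simulated trials per setting. The paired t-test is on the raw scale. The between-arm comparison is ANCOVA of log value on log baseline and arm.

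**1. Shared rise, no arm difference.** Any rejection in the ANCOVA column is a false positive; the paired tests respond to the shared rise.

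| Shared rise | Within-patient SD | Paired, Arm 2 | Paired, pooled | Arm 2 significant, Arm 1 not | ANCOVA |
|---|---|---|---|---|---|
| 20% | 1.2 | 91.9% | 99.7% | 7.8% | 4.9% |
| 20% | 1.35 | 52.5% | 82.3% | 25.0% | 4.9% |
| 20% | 1.5 | 31.5% | 56.0% | 21.5% | 4.9% |
| 10% | 1.2 | 42.1% | 71.7% | – | 4.9% |
| 10% | 1.35 | 18.2% | 32.9% | – | 4.7% |
| 10% | 1.5 | 12.1% | 19.7% | – | 4.9% |

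A hand check on the log scale: noncentrality = ln(1.2) × √30 / (√2 × ln SD). For SD 1.35 this is 0.182 × 5.48 / 0.424 = 2.35, and the noncentral t with 29 df gives 62%. For SD 1.2 and 1.5 it is 3.87 and 1.74, giving 96% and 39%. The log scale raises the figures slightly and the conclusion is the same.

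**2. No drift, real Arm 2 effect.** For SD 1.2/1.35/1.5, a 1.25-fold effect is detected by the paired test in 98.2/69.7/43.7% and by ANCOVA in 92.4/57.4/37.8%. For a 1.2-fold effect the figures are 91.3/53.1/32.0% and 79.1/41.9/27.1%. Here the paired test does better.

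**3. Precision of the ANCOVA ratio.** Half-width on the log scale ≈ 2.00 × σ × √(2/30), with σ² = (b² + w²)(1 − ρ²), ρ = b²/(b² + w²), b = ln 1.6, w = ln SD. For SD 1.35: b² = 0.221, w² = 0.090, ρ = 0.71, σ = 0.393. The half-width is 0.203, a factor of 1.23. For SD 1.2 and 1.5 the factors are 1.14 and 1.30. With 20 per arm the range is 1.17-1.39.

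**4. Exposure at candidate visits.** Cycle 3 day 1 is day 43, 14 days after the cycle 2 day 8 dose (day 29). Before dosing that day, Arm 2 has had 4 pTVG-AR doses and Arm 1 has had 4 pTVG-HP, with 2 pembrolizumab doses each. Cycle 7 day 1 is day 127: 8 pTVG-AR plus 4 pTVG-HP against 12 pTVG-HP. The first on-study scan is at cycle 5 day 1 (day 85). With the median time to progression of about 3 months in section 2.G and an exponential assumption, 0.5^(18/13) ≈ 38% are progression-free at week 18. Treatment may continue past the 3-month scan, so this is a lower guide to retention.

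**5. Multiplicity.** Four independent tests at 0.05: 1 − 0.95⁴ = 18.5%. At correlation 0.5 it is 15.6%.

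**The case against.** A reader might infer that CK and liver injury are never compared between the randomised arms. The documents do not support that. Fisher's test covers any CK, AST, ALT or bilirubin abnormality recorded as a toxicity, and section 13.A leaves out only findings that are both grade 1-2 and judged insignificant. The gap is continuous change below that threshold.

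Next, section 11.w.i announces laboratory comparisons and a later SAP, so a between-arm analysis may still come. That is fair, and it is the natural place for the fix. As written, though, the only test named for chemistry change is the paired one.

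Section 14 also describes monitoring of individual patients, not an endpoint for comparing arm means. That stands, and it limits the importance of the point.

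A further objection is that immune injury would probably affect a few patients rather than shift a mean. This also stands: on the same assumptions, with 3 of 30 Arm 2 patients having a 3- to 5-fold rise, ANCOVA has only about 9-19% power. A shift table suits that pattern better and should be the main change.

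Finally, the illustrated size depends on an assumed shared drift. With none and no effect, the paired test rejects at about 5%; with none and a real Arm 2 effect, it has more power than ANCOVA.

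**Conclusion.** The point holds in limited form and is minor. F.5.4 compares graded toxicities between arms but names only a before/after test for continuous chemistry change. For changes below the adverse-event threshold in CK and the liver tests, that test cannot tell an arm difference from what both arms share. This follows from the design and needs no assumed SD. The size does: under the assumptions above, a shared 20% rise with no arm difference makes the Arm 2 paired test significant in about 32-92% of trials and the pooled test in 56-100%, against 5% for the between-arm comparison.

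Two stronger readings fail. Patient safety is not weakened: grade-based dosing rules and per-arm stopping boundaries do not use this test, and the primary endpoint and sample size are untouched. Nor would a between-arm comparison isolate the AR vaccine. Over eight cycles Arm 2 gets 8 pTVG-AR plus 8 pTVG-HP doses against 16 pTVG-HP in Arm 1, so AR exposure comes with fewer pTVG-HP doses.

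**What to change.** In F.5.4 or the detailed SAP:

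- **(a)** Report paired changes by arm, as descriptive only.
- **(b)** As the main change, add a by-arm table of shift from baseline to worst on-treatment value (CTCAE grade or multiple of ULN). Use all laboratory values, whether or not recorded as adverse events, with the Wilson intervals already planned.
- **(c)** As a supportive estimate for CK, AST, ALT and total bilirubin, give the between-arm geometric mean ratio with 95% CI from baseline-adjusted log ANCOVA at two visits. Read cycle 3 day 1 as 4 pTVG-AR against 4 pTVG-HP doses, each with pembrolizumab; no Arm 2 patient has yet had both vaccines. Read cycle 7 day 1 as the two-vaccine exposure, with more dropout.

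The cost is SAP wording and a few tables; the panel, which includes CK, is already drawn on day 1 of each cycle. The downsides are less power than the paired test when there is no drift, little power for rises in a few patients, and a 16-19% chance of at least one false positive across four unadjusted tests at one visit, more with two. For that reason (c) should report estimates and intervals rather than significance.
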